#### 6. DOSE MODIFICATIONS

Individually, each subject will be allowed up to dose-reduce to 75 mg infigratinib, as follows (see also Table 5).

- If a subject's infigratinib dose is 125 mg, 2 dose reductions of infigratinib are permitted.
- If a subject's infigratinib dose is 100 mg, 1 dose reduction of infigratinib is permitted.
- If a subject's infigratinib dose is 75 mg, no dose reduction of infigratinib is permitted, with infigratinib treatment discontinuation the only option.

Subjects should discontinue infigratinib if toxicities persist following dose reductions to the lowest level allowed, unless it has been discussed and approved by the QED Therapeutics' Medical Monitor.

Following resolution of toxicity to baseline or  $\leq$  Grade 1, or  $\leq$  Grade 2 for hematologic toxicities, treatment is resumed at either the same or lower dose of study drug as per the criteria in Table 6. Adverse event lab abnormalities outlined in Table 6 should be followed at least weekly until the specified resolution. If treatment is resumed at the same dose of study drug, and the same toxicity recurs with the same or worse severity regardless of duration, dose must be reduced to the next lower dose level. If treatment is resumed at the lower dose of study drug, and the same toxicity recurs with the same or worse severity, the subject should have a second dose reduction.

Subjects who are withdrawn from the study for a study related AE or an abnormal laboratory value must be followed as described in Section 7.3.

**Table 5.** Dose Modification Scheme for Infigratinib

Dose Reduction			
	Dose level 3	(Starting) Dose level 2	Dose level 1
Infigratinib	125 mg	100 mg	75 mg

In exceptional situations, study drug may continue even if the subject experienced one of the treatment stopping rules. The decision to allow for continuation of treatment will be made on a case-by-case basis following discussion between QED Therapeutics and the investigator.

**Table 6.** Criteria for Interruption and Re-initiation of Infigratinib for AEs Considered to be Possibly Related to Infigratinib

Worst Toxicity CTCAE (v5.0) Grade (Unless Otherwise Specified)	Recommended Dose Modifications any Time During a Cycle of Therapy					
CARDIAC DISORDERS						
Cardiac - Prolonged QTcF Interv	Cardiac - Prolonged QTcF Interval					

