Grade 1 and 2: QTcF ≥ 481msec and ≤ 500 msec (asymptomatic)	
 
Maintain dose level of infigratinib.
 
Two additional ECGs separated by at least 5 minutes should be performed to confirm the finding. If the finding is confirmed, single ECG assessments should be performed every 2 weeks for 2 additional cycles, or as clinically indicated. If abnormality is detected, 2 additional ECGs separated by at least 5 minutes should be performed to confirm the finding.
 
If ECG assessments show no QTcF ≥ 481 msec, for subsequent cycles ECG monitoring will be performed at each subsequent visit, per visit schedule.
 
If ECG assessments are still abnormal (QTcF ≥ 481 msec and ≤ 500 msec), then ECG monitoring must continue every 2 weeks for all subsequent cycles.
 
					
Grade 3: QTcF > 500msec or > 60 ms change from baseline as identified on the ECG by the investigator	
 
Hold infigratinib. Two additional ECGs separated by at least 5 minutes should be performed to confirm the finding. If the finding is confirmed, the subject should be admitted to the hospital for at least 24 hours of continuous telemetry; once confirmed no further prolongation of QTc and no arrhythmias over 24 hour period, subject can be discharged. After discharge, subject should return to clinic weekly for ECG until normalization.
 
Exclude other causes of QTcF prolongation such as hypokalemia, hypomagnesaemia, and decreased blood oxygenation.
 
Subjects should receive appropriate electrolyte replacement and should not receive further infigratinib until electrolytes are documented to be within normal limits.
 
Once the QTcF prolongation has resolved, subjects may be re-treated at one lower dose level at the investigator's discretion.
 
					

**Table 6.** Criteria for Interruption and Re-initiation of Infigratinib for AEs Considered to be Possibly Related to Infigratinib

	Possibly Related to Illigratifib					
Worst Toxicity CTCAE (v5.0) Grade (Unless Otherwise Specified)	Recommended Dose Modifications any Time During a Cycle of Therapy					
Grade 3: QTcF > 500msec or > 60 ms change from baseline as identified on the ECG by the investigator (continued)	Single ECG assessments should be performed for 2 additional cycles every 2 weeks or as clinically indicated. If abnormality is detected, 2 additional ECGs separated by at least 5 minutes should be performed to confirm the finding.					

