	
 
If ECG assessments show no QTcF ≥ 481 msec, ECG monitoring will be performed at each subsequent visit, per visit schedule for subsequent cycles.
 
					
	
 
If ECG assessments are still abnormal (QTcF ≥ 481 msec and ≤ 500 msec), then ECG monitoring must continue every 2 weeks or as clinically indicated, for all subsequent cycles.
 
					
	
 
Subjects who experience recurrent QTcF ≥ 500msec after one dose reduction will be withdrawn from study.
 
					
	If QTcF > 500 msec or > 60 msec change from the baseline is observed, a plasma sample for determination of infigratinib concentration should be obtained with the time of sample collection noted.					
Grade 4: Torsade de pointes or polymorphic ventricular tachycardia or signs/symptoms of serious arrhythmia	Discontinue infigratinib.  A plasma sample for determination of infigratinib concentration should be obtained with the time of sample collection noted.					
Cardiac Disorders - Others						
Grade ≥ 3 OR Congestive heart failure Grade ≥ 2	Discontinue infigratinib.					
	INVESTIGATIONS-HEMATOLOGY *					
ANC Decreased (Neutropenia)*						
Grade 3 (ANC < 1.0 to 0.5 × 10  /L)	Hold dose of infigratinib until resolved to CTCAE Grade ≤ 2 or baseline, then					
	
 
If resolved within ≤ 7 days, maintain dose level of infigratinib
 
					
	If resolved between > 7 days and 14 days, decrease by     dose level of infigratinib					
	If not resolved within ≤ 14 days, discontinue infigratinib					
Grade 4 (ANC < 0.5 × 10  /L)	Hold dose of infigratinib until resolved to CTCAE ≤ Grade 2, decrease by 1 dose level of infigratinib					
	If not resolved within ≤ 14 days, discontinue infigratinib					

**Table 6.** Criteria for Interruption and Re-initiation of Infigratinib for AEs Considered to be Possibly Related to Infigratinib

Possibly Related to Illigratifie						
Worst Toxicity CTCAE (v5.0) Grade (Unless Otherwise Specified)	Recommended Dose Modifications any Time During a Cycle of Therapy					
of Neutropenia": that is, if any of the present – sepsis syndrome, age > 0	nistering G-CSF per NCCN guidelines (Version 2.2019) "Management be following risk factors for an infection-associated complication are 65 years, ANC < 100/mcL, clinically documented infection, invasive time of fever, or prior episode of febrile neutropenia.					

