Grade 2 (≥ 2.00 to 3.0 × ULN or 2.0 to 3.0 × baseline)	
 
Hold dose of infigratinib until resolved to Grade ≤ 1 or baseline
 
If resolved within ≤ 7 days, maintain dose level of infigratinib
 
If resolved between > 7 days and 14 days, decrease by 1 dose level of infigratinib
 
If not resolved within ≤ 14 days, discontinue infigratinib
 
					
Grade ≥ 3 (> 3.0 × ULN or > 3 × baseline)	Discontinue infigratinib					
	INVESTIGATIONS – HEPATIC					
AST or ALT						
Grade 3 (> 5.0 to 20.0 × ULN) without bilirubin elevation > 2.0 × ULN	Hold dose of infigratinib until resolved to CTCAE Grade ≤ 1 or baseline  • If resolved within ≤ 7 days, decrease by 1 dose level of infigratinib  • If not resolved within ≤ 7 days, discontinue infigratinib					
Grade 4 (> 20.0 × ULN) without bilirubin elevation > 2.0 × ULN	Discontinue infigratinib					
AST or ALT and Bilirubin						
AST or ALT > 3.0 to 5.0 × ULN and total bilirubin > 2.0 × ULN without liver metastasis or evidence of disease progression in the liver	
 
Hold dose of infigratinib until both transaminases and bilirubin resolved to CTCAE Grade ≤ 1 or baseline.
 
If resolved within ≤ 7 days, decrease by 1 dose level of infigratinib.
 
If not resolved within ≤ 7 days, discontinue infigratinib
 
					
AST or ALT > 5.0 × ULN and total bilirubin > 2.0 × ULN	Discontinue infigratinib					

**Table 6.** Criteria for Interruption and Re-initiation of Infigratinib for AEs Considered to be Possibly Related to Infigratinib

Worst Toxicity CTCAE (v5.0) Grade (Unless Otherwise Specified)	Recommended Dose Modifications any Time During a Cycle of Therapy						
LABORATORY / METABOLIC DISORDERS							
Asymptomatic Amylase and/or I	ipase Elevation						
present, consider a CT scan or oth	nptoms of acute pancreatitis (abdominal pain or tenderness), and, if er imaging study to assess the pancreas, liver, and gallbladder to creatitis and assess for complications.						
Grade 3 (> 2.0 to 5.0 × ULN)	Hold dose of infigratinib until resolved to CTCAE Grade ≤ 2						
	decrease by 1 dose level of infigratinib						
	
 
If not resolved within ≤ 14 days, discontinue infigratinib
 
						
	For recurrent Grade 3 asymptomatic lipase or amylase elevation despite dose reduction, infigratinib should be held and continuation of therapy should be discussed with the medical monitor following resolution to ≤ Grade 2.						

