Any Grade ≥ 3 neurotoxicity	Discontinue infigratinib
•	STROINTESTINAL SYSTEM DISORDERS
Pancreatitis	
Grade ≥ 2	Discontinue infigratinib
Diarrhea	
General Comment:	Antidiarrheal medication is recommended at the first sign of abdominal cramping, loose stools or overt diarrhea
Grade 1	Maintain dose level of infigratinib, initiate anti-diarrheal treatment
Grade 2	
 
Hold dose of infigratinib until resolved to CTCAE Grade ≤ 1
 
Optimize anti-diarrheal treatment
 
For reoccurrence of diarrhea CTCAE Grade 2, hold dose of infigratinib until resolved to CTCAE Grade ≤ 1, decrease infigratinib by 1 dose level
 

Grade 3	
 
Hold dose of infigratinib until resolved to CTCAE Grade ≤ 1
 
Optimize anti-diarrheal treatment
 
Decrease infigratinib by 1 dose level
 
For reoccurrence of diarrhea CTCAE Grade 3, despite optimal antidiarrheal treatment, discontinue infigratinib
 

Grade 4	Discontinue infigratinib

**Table 6.** Criteria for Interruption and Re-initiation of Infigratinib for AEs Considered to be Possibly Related to Infigratinib

	1 033ibly Related to Imigratinib					
Worst Toxicity CTCAE (v5.0) Grade (Unless Otherwise Specified)	Recommended Dose Modifications any Time During a Cycle of Therapy					
Vomiting						
Grade 2 not controlled by optimal anti-emetic therapy	Hold infigratinib doses until ≤ Grade 1, decrease by 1 dose level • If not resolved within ≤ 14 days, discontinue infigratinib					
Grade 3 not controlled by optimal anti-emetic therapy, or Grade 4	Discontinue infigratinib					
EYE DISORDERS	(CONFIRMED BY OPHTHALMOLOGIC EXAMINATION)					
Retinal Disorders						
Grade 2 central serous retinopathy and central serous retinopathy -like events	Hold infigratinib until resolved to ≤ Grade 1 and continue ophthalmologic evaluation  • If resolved within ≤ 14 days, decrease infigratinib by 1 dose level  • If resolved after > 14 days, discontinue infigratinib					
Grade ≥ 1 retinal vein occlusion, Grade 3 or 4 central serous retinopathy and central serous retinopathy-like events, and Grade 3 or 4 other eye disorders	Discontinue infigratinib					
Other Ocular/Visual Toxicity						
Grade ≥ 3	Discontinue infigratinib  •					
	SKIN DISORDERS					
Palmar-plantar erythrodysesthes	sia syndrome					
Grade 3	Hold dose of infigratinib until resolved to Grade ≤ 1, and then resume infigratinib at decrease by 1 dose level					
Paronychia						

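### The Section 6 recurrence sentences call for a dose reduction where some Table 6 rows stop infigratinib, and no text says which governs (minor, low frequency)

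*Combined protocol and SAP*

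**What the plan says.** The text of Section 6 (Dose Modifications) has two general recurrence rules.

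- After resumption at the same dose, if "the same toxicity recurs with the same or worse severity regardless of duration, dose must be reduced to the next lower dose level".
- After resumption at a lower dose, if "the same toxicity recurs with the same or worse severity, the subject should have a second dose reduction".

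Neither rule names an exception. Section 6 permits two reductions from 125 mg, one from 100 mg and none from 75 mg.

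Table 6, in the same section, has its own instructions for some of these events.

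- Diarrhea Grade 3: the first episode already requires a one-level decrease. Then: "For reoccurrence of diarrhea CTCAE Grade 3, despite optimal antidiarrheal treatment, discontinue infigratinib".
- QTcF Grade 3: "Once the QTcF prolongation has resolved, subjects may be re-treated at one lower dose level at the investigator's discretion". Then: "Subjects who experience recurrent QTcF ≥ 500msec after one dose reduction will be withdrawn from study".
- Asymptomatic lipase or amylase Grade 3: the first episode requires a one-level decrease. A recurrence goes to the medical monitor: "For recurrent Grade 3 asymptomatic lipase or amylase elevation despite dose reduction, infigratinib should be held and continuation of therapy should be discussed".
- Calcium and creatinine: a Grade 2 event that resolves within 7 days resumes at the same dose. Grade 3 or worse is discontinued.
- Rows that discontinue at a higher grade include AST/ALT "Grade 4 (> 20.0 × ULN) without bilirubin elevation > 2.0 × ULN" and "Any Grade ≥ 3 neurotoxicity".

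Section 6 cites Table 6 for the dose at which treatment resumes and for weekly follow-up of laboratory abnormalities. It also lets treatment continue past a stopping rule in exceptional cases, after discussion between the supplier and the investigator.

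**The concern.** A site managing a second episode has two instructions in one section. Followed literally, the general sentences lower the dose and keep the subject on infigratinib, while the table row stops the drug or adds a discussion step. One of the rows is cardiac. In the monotherapy data in Section 2.2.9, no QT event was serious or led to withdrawal or a dose change. However, every subject here also takes tamoxifen, which Appendix B lists among drugs with possible QT or torsades risk, so that record may not carry over to the combination.

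The path is open by design. Under Section 12.4, a subject with no DLT after two cycles at 100 mg moves to 125 mg, and from there two reductions are available.

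**Working it through.** **Step 1. Where do the instructions differ?**

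| Path | Section 6 text | Table 6 |
|---|---|---|
| 125 → 100 mg, Grade 3 diarrhea recurs despite optimal treatment | second reduction, to 75 mg | discontinue |
| 125 → 100 mg, QTcF ≥ 500 msec recurs | second reduction, to 75 mg | withdraw |
| 125 → 100 mg, Grade 3 lipase/amylase recurs | second reduction, to 75 mg | hold, discuss continuation |
| Same-dose resumption (125 or 100 mg), calcium Grade 2 then ≥ 3 | reduce one level | discontinue |
| Same-dose resumption (125 or 100 mg), creatinine Grade 2 then ≥ 3 | reduce one level | discontinue |
| 125 → 100 mg, AST/ALT Grade 3 then 4, or neurotoxicity Grade 2 then ≥ 3 | second reduction, to 75 mg | discontinue |

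The second-reduction sentence can be carried out only in a subject reduced from 125 to 100 mg. A subject reduced from 100 to 75 mg has no reduction left, and Section 6 itself then stops the drug unless the supplier's medical monitor approves continuing. The same-dose sentence can also apply at the 100 mg starting dose.

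**Step 2. Does any text set precedence?** No. The references to Table 6 cover the resumption dose and laboratory follow-up. The exceptional-situations sentence implies that stopping is the default, but it does not mention recurrence.

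**Step 3. How many subjects could be at 125 mg?** From Section 12.4:

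- 0 to 2 if the first three have DLTs at 100 mg;
- 3 if all three escalate with no DLT;
- 3 + 3 = 6 if one then has a DLT at 125 mg;
- 5 + 3 = 8 if one of six has a DLT at 100 mg, five escalate and three are added (an assumption).

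The working range is therefore 0 to about 8.

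**Step 4. Rates.** These come from the monotherapy data at 125 mg in Section 2.2.9 and its Table 2 (N = 433). The stated percentages reproduce: QTc > 500 msec 3/433 = 0.69% (stated 0.7%); Grade 3–4 diarrhea 9/433 = 2.08% (2.1%); lipase 27/433 = 6.24% (6.2%); hypercalcemia 14/433 = 3.23% (3.2%).

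**Step 5. Expected first events = n × rate.**

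| Event | n = 0 | n = 6 | n = 8 |
|---|---|---|---|
| QTc > 500 msec (0.7%) | 0 | 0.04 | 0.06 |
| Diarrhea Grade 3–4 (2.1%) | 0 | 0.13 | 0.17 |
| Lipase Grade 3–4 (6.2%) | 0 | 0.37 | 0.50 |
| Sum (9.0%) | 0 | 0.54 | 0.72 |

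Only recurrences trigger the conflict. The documents give no recurrence rate. If 10% to 50% recur (an assumption), the three rows together give 0.05 to 0.27 recurrences at n = 6 and 0.07 to 0.36 at n = 8. The chance of at least one at n = 6 runs from 1 − (1 − 0.009)^6 = 5% to 1 − (1 − 0.045)^6 = 24%.

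For the same-dose path at any dose, with 3 to 12 evaluable subjects, Grade 3–4 hypercalcemia is expected in 3 × 3.2% = 0.10 to 12 × 3.2% = 0.38 subjects. That is an upper limit, because only events that follow a resolved Grade 2 episode count. Grade 3–4 creatinine is absent from Table 2, which lists events at 1.0% or more, so 12 subjects would give fewer than about 12 × 1.0% = 0.12.

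**The case against.** **Stopping is already the default.** Section 6 allows treatment past a stopping rule only exceptionally and after discussion. This is a fair inference and it lowers the risk. It still leaves the general sentences without an exception, and the second-reduction sentence continues treatment with no discussion.

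**The table row is in front of the site.** Table 6 is keyed to worst grade at any time in a cycle, so a recurrence at a higher grade falls in its own discontinue row. The QTcF row likewise carries the withdrawal instruction. This stands as a mitigation. The worse-grade paths are therefore weaker examples than recurrent diarrhea and QTcF.

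**The wording is softer than it looks.** The second-reduction sentence says should; only the same-dose sentence says must. This also stands. The lipase/amylase row does not forbid a lower dose after the discussion, so there Section 6 omits a step and does not give an opposite instruction.

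**A stronger reading to resist: hyperphosphatemia.** A reader might infer that reducing regardless of duration contradicts the phosphorus row, which depends on level, duration and binder dose. The documents do not support this. The phosphorus row has no recurrence rule, and the Section 6 sentence can be read as a deliberately stricter rule for a second episode. Grade 3 anemia has the same form: Table 6 says hold and then maintain the dose, and Section 6 adds a reduction on recurrence. In addition, the sevelamer steps in Section 4.1.2 and the increased binder on restart in Table 6 normally bring a subject to 1600 mg three times daily by a recurrence. For a lasting recurrence at that binder dose, Table 6 also reduces. Exempting phosphorus would be a clinical policy choice.

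**Conclusion.** The text is wrong as written, but the point is minor and of low frequency. The clear conflicts are recurrent Grade 3 diarrhea and recurrent QTcF after a reduction from 125 to 100 mg, and calcium or creatinine going from Grade 2 to Grade 3 or worse after same-dose resumption. Lipase/amylase is an omitted hold-and-discuss step. Other worse-grade recurrences are similar but better covered by their own rows.

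Expected numbers are well under one for each row. This rests on monotherapy rates carrying over to the combination and to doses below 125 mg, on 0 to about 8 subjects at 125 mg, and on an assumed recurrence share.

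A reader might infer that the dose recommendation is affected. The documents do not show that: Table 7 defines DLTs by events and by missed or delayed doses, and nothing here shows that the choice of recurrence rule changes the count.

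**What to change.** Add one clause to both recurrence sentences in Section 6: *unless Table 6 requires discontinuation, withdrawal, or a hold with medical monitor discussion for that event, its grade, or its recurrence, in which case Table 6 applies.*

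All other recurrences, including phosphorus and Grade 3 anemia, stay under the Section 6 rule. Table 6, the sample size and the visit schedule do not change. The cost is one clause in two sentences at the next amendment.

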#### 4. TREATMENT PLAN

Potential subjects who preliminarily meet inclusion criteria and exclusion criteria as determined by study staff (for example, the investigator or clinical research coordinator) will meet with study staff to review the study and informed consent in detail. At this time, inclusion and exclusion criteria will be confirmed with the subjects and treating clinicians as necessary.

All eligible subjects (meeting criteria described in Section 3) will receive the drug combination of infigratinib with tamoxifen. Once a dose level for infigratinib is determined, Cohort 1 will close.

All subjects in whom a research biopsy of a disease site is deemed feasible and safe by the investigator will be required to undergo a biopsy to donate 4 to 8 cores of tumor tissue before and on-treatment to be used for research purposes, including genomic/transcriptomic/proteomic analysis and organoid culture derivation as described in Section 2.6. The on-treatment biopsy is recommended to occur on Day 15 of treatment, but any time on treatment is acceptable. Tissue will be transported to the [name] lab for processing and analysis. Subjects who require a tumor biopsy for eligibility assessment will undergo the collection of tissue cores for research simultaneously, whenever possible. Archival tumor tissue, including stored at Stanford University and at other institutions, may be obtained for use for tissue correlative studies as well. Only tissue not needed for diagnostic purposes will be used for research.

Subjects in Cohort 1 will receive tamoxifen 20 mg orally continuously starting on Day 1 and will additionally receive infigratinib orally daily 3 weeks on, 1 week off (28-day cycle) at the dose level dictated by study protocol (125 mg, 100 mg, or 75 mg).

Subjects will continue receiving cycles as above until 18 months on treatment, progression, or unacceptable toxicity (or other reasons outlined in Section 4.3). If toxicity is deemed per the investigator to be related to endocrine therapy (tamoxifen) and not infigratinib, subjects will be given the option of continuing infigratinib only (without endocrine therapy) until progression.

Details on study procedures during Screening, Treatment, and Post-Treatment are provided in the Study Calendar and footnotes (Section 9).

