APPENDIX B: List of drugs to be used with caution while on study

Category	Drug Names		
CYP3A substrates with narrow therapeutic index	alfentanil, cyclosporine, diergotamine, dihydroergotamine, ergotamine, fentanyl, sirolimus, tacrolimus, terfenadine, warfarin sodium or any other coumadin-derivative anticoagulants, direct thrombin inhibitors (eg, argatroban), and Factor Xa inhibitors (eg, rivaroxaban)		
Moderate inhibitors of CYP3A4	amprenavir, aprepitant, atazanavir, cannabinoids, casopitant, cimetidine, ciprofloxacin, darunavir, diltiazem, fosamprenavir, imatinib, metronidazole, Schisandra sphenanthera, sertraline, suboxone, tofisopam, verapamil, zafirlukast		
Moderate inducers of CYP3A4	bosentan, cotrimoxazole, efavirenz, etravirine, ethosuximide, genistein, metyrapone, mexiletine, modafinil, nafcillin, talviraline, tipranavir		
Medications which alter the pH of the GI tract a,b	antacids, H₂antagonists (eg, ranitidine), proton-pump inhibitors (eg, omeprazole)		
Medications that have possible risk of TdP/QT prolongation	alfuzosin, amantadine, atazanavir, chloral hydrate, clozapine, dolasetron, eribulin, famotidine, felbamate, fingolimod, foscarnet, fosphenytoin, gatifloxacin, gemifloxacin, granisertron, iloperidone, indapamide, isradipine, lapatinib, lithium, moexipril, nicardipine, nilotinib, octreotide, ofloxacin, ondansetron, oxytocin, paliperidone, pasireotide, quetiapine, ranolazine, risperidone, roxithromycin, sertindole, sunitinib, tamoxifen, tizanidine, vardenafil, venlafaxine, ziprasidone		
Medications that have conditional risk of TdP/QT prolongation	amitriptyline, amisulpride, ciprofloxacin, clomipramine, desipramine, diphenhydramine, doxepin, fluoxetine, galantamine, imipramine, nortriptyline, paroxetine, protriptyline, sertraline, solifenacin, trazodone, trimethoprim-sulfa, trimipramine		
BCRP substrates	atorvastatin, irinotecan, methotrexate, rosuvastatin, simvastatin, sulfasalazine, topotecan		

Abbreviations: BCRP, breast cancer resistance protein; CYP, cytochrome p; F DA, Food and Drug Administration; GI, gastrointestinal; TdP, Torsades de Pointes

<sup>a Infigratinib should be dosed at least 2 hours before or 10 hours after dosing with a gastric protection agent.

b If possible, proton pump inhibitors should be avoided due to their long pharmacodynamic effect and replaced with H2 antagonists or antacids.

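### Table 6 opens the Grade 3 QTcF row on an absolute value or a change from baseline, but tests step-down, persistence and recurrence on absolute values alone

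*Combined protocol and SAP*

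**What the plan says.** All the relevant text is in the QTcF block of Table 6, Section 6.

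- **Entry to Grade 3:** "Grade 3: QTcF > 500msec or > 60 ms change from baseline as identified on the ECG by the investigator". Infigratinib is held and two further ECGs are taken. Only then: "If the finding is confirmed, the subject should be admitted to the hospital for at least 24 hours of continuous telemetry".
- **Maintain-dose row:** "Grade 1 and 2: QTcF ≥ 481msec and ≤ 500 msec (asymptomatic". It sets no condition on change from baseline.
- **Step-down inside the Grade 3 row:** "If ECG assessments show no QTcF ≥ 481 msec, ECG monitoring will be performed at each subsequent visit, per visit schedule".
- **Persistence inside the Grade 3 row:** "If ECG assessments are still abnormal (QTcF ≥ 481 msec and ≤ 500 msec), then ECG monitoring must continue every 2 weeks".
- **Recurrence inside the Grade 3 row:** a recurrent QTcF of 500 msec or more after one dose reduction means withdrawal from study.
- **Plasma sample inside the Grade 3 row:** triggered by more than 500 msec or a change of more than 60 msec, so both criteria are kept here.

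The table's column heading tells the reader to act on the worst toxicity grade, unless otherwise specified. Exclusion criterion 12d in Section 3.2 admits a baseline QTcF of up to 470 msec.

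**The concern.** The row has two ways in, but three of its follow-up sentences recognise only one. A subject who entered on change from baseline may never have reached 481 msec, so the step-down sentence can be satisfied although nothing has improved. The plasma-sample sentence keeps both criteria, so the row itself gives no sign that the change criterion was meant to lapse after onset.

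At stake is consistent cardiac monitoring. Read literally, the text moves such a subject from ECGs every 2 weeks to ECGs at visits. From Cycle 3 the Section 9 visits fall on Day 1 of each 28-day cycle, so the interval doubles to 4 weeks. It becomes longer still if the sparser ECG row of the Section 9 calendar is meant. At 500 msec exactly, onset and recurrence also disagree on whether the value is an event, and the recurrence sentence leads to withdrawal.

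**Working it through.** The plan gives no figure to reproduce here, so the check applies the printed rules to pairs of values. Let b be the baseline QTcF and q the on-treatment QTcF, both in whole msec, with b ≤ 470 (Section 3.2).

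| Rule in Table 6 | Condition |
|---|---|
| Grade 3 entry | q > 500 or q − b > 60 |
| Maintain-dose row | 481 ≤ q ≤ 500 |
| Step-down | q ≤ 480 |
| Still abnormal | 481 ≤ q ≤ 500 |
| Recurrence (after one reduction) | q ≥ 500 |

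**1. Grade 3 label and step-down together.** This needs q ≤ 480 and q − b > 60, so b < 480 − 60 = 420.
- 410 to 475 is +65: Grade 3 by change, step-down met, not counted as still abnormal.
- 419 to 480 is +61: the same result, at the upper edge.
- 420 to 480 is +60: no longer Grade 3.

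**2. Exactly 500 msec.** From b = 470 (+30) or b = 440 (+60), q = 500 is not Grade 3 and sits in the maintain-dose row. After a dose reduction the same value meets the recurrence rule. Conversely, 410 to 475 recurring after a reduction is Grade 3 by change but is missed by the recurrence sentence. It is left to Section 6's general rule on recurring toxicity.

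**3. Maintain-dose and Grade 3 rows together.** This needs 481 ≤ q ≤ 500 and q − b > 60. At q = 500, b < 440; at q = 481, b < 421. So for b below 421 the whole 481 to 500 range is in both rows, and for b from 421 to 439 only its upper part is. Example: 430 to 491 is +61.

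**4. Enumeration.** All integer pairs were listed with b from 350 to 470 (the lower limit is an assumption) and q from b to 559. The highest baseline with overlap is 419 in step 1 and 439 in step 3. No pair meets Grade 3, maintain-dose and step-down together.

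**5. Expected frequency.** Section 2.2.9 reports a QTcF change above 60 msec in 4 subjects (1.0%) on monotherapy. The synopsis plans up to 12 evaluable subjects.
- Expected number: 12 × 0.010 = 0.12.
- Chance of at least one: 1 − 0.99^12 = 0.11.

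These assume that the monotherapy rate carries over. The documents give no rate for the combination with tamoxifen.

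**The case against.** The strongest reply is that earlier steps protect the subject. A confirmed Grade 3 event means infigratinib is held, the subject is admitted, and ECGs are weekly until they normalise. Re-treatment follows only after resolution, and Section 6 generally requires return to baseline or Grade 1 or lower. A subject still at +65 msec has arguably not resolved. If the change reappears on treatment, the Grade 3 row applies again, because Table 6 covers any time in a cycle.

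Much of this stands: the step-down governs ECG frequency, not dosing. It does not cure the text, because neither normalisation nor resolution has a QTcF value, and Table 6 merges Grades 1 and 2 into one range. The worst-toxicity heading cannot help either, since entry and step-down sit in the same row. On recurrence, a stricter limit after an earlier event could be deliberate, but the row does not say so and omits the change criterion.

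Several stronger readings are tempting but unsupported:

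- **One ECG could mean hold, maintain or all-clear.** Maintain needs at least 481 msec and step-down needs less, so at most two of the three apply. Admission also needs confirmation by two further ECGs.
- **Hold and maintain are in open conflict at onset.** The heading points to Grade 3, so this is a loose boundary.
- **The criterion dropped at follow-up was the commoner one in earlier data.** Section 2.2.9 gives 4 subjects with a change above 60 msec and 3 above 500 msec. The follow-up tests 481 msec, for which no rate is given, and the two groups may overlap.
- **Missed doses from a hold would distort the DLT count.** The first scheduled on-treatment ECG is Cycle 2 Day 1, whereas the missed-dose criterion in Table 7 counts Cycle 1 days.
- **Silence on tamoxifen is a contradiction.** Appendix B lists it under "Medications that have possible risk of TdP/QT prolongation", and Section 4 has a rule that begins "If toxicity is deemed per the investigator to be related to endocrine therapy (tamoxifen) and not infigratinib". But Table 6 is written for infigratinib throughout, and Appendix B drugs are allowed with caution. A tamoxifen instruction would be a new clinical rule.

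**Conclusion.** The inconsistency is real and lies within one row. Two criteria define the Grade 3 event and trigger the plasma sample, while step-down, persistence and recurrence use absolute values only. It can affect any eligible subject with a baseline below 420 msec. Separate, smaller faults are the boundary at exactly 500 msec and the unstated precedence between the maintain-dose and Grade 3 rows for baselines below 440 msec.

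The practical size is small. About 0.12 subjects with a change above 60 msec are expected among 12, on the assumption that the monotherapy rate applies. Section 2.2.9 adds that none of the earlier QT events was serious or led to interruption, dose reduction or withdrawal. The case for correction rests on clear safety instructions, not on an effect on the trial's estimates. The documents do not show which threshold was intended, and this review takes no position on that.

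**What to change.** Reconcile the QTcF rows of Table 6:

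- Use one stated definition of an abnormal QTcF at onset, step-down, persistence and recurrence, or say explicitly where a criterion is meant to differ and why.
- Settle how a value of exactly 500 msec is classed, so that the maintain-dose range and the recurrence rule agree.
- Make the maintain-dose and Grade 3 rows mutually exclusive, or state in the row that the higher grade governs when both are met.

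The sponsor and investigator decide which thresholds and actions apply. The cost is an edit to one block of one table in the next amendment. Reconciling the wording does not by itself require extra ECGs, visits or subjects; any change in monitoring would follow from the definition they choose.
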